Statistical blinding will be assured to generate summary variables and set the final analysis for between group differences. Once the final statistical coding is defined and validated by the TSC, the true group identity will be revealed and additional descriptive information on treatment will be provided.

- Coding allocation to random A, B to blind first step of statistical analysis
- Treatment description included in separate dataset to be coded with different IDS than main dataset.

5. Outcome measures

Primary Outcome measure

Crying time diary

The main outcome is daily crying time in minutes. This can be measured for crying times from the first day after treatment to the thirteenth day after treatment. Daily crying time is obtained by adding hourly reported crying times from 6AM to 5:59AM the next day. D-1 is computed from the hourly reported crying time on the day prior to the treatment if the entire day is completed. When incomplete, it is replaced by the parent reported 24h baseline crying time (castor.csv). Daily crying time is considered as missing if any of the time hour slots has missing values within the day.

The primary outcome is the between group average difference in crying time from day 1 after the treatment to day 13 after the treatment. Repeated measures random linear mixed effect adjusting for baseline crying time, expectations for treatment outcome and infant's age is used to estimate the between group difference.

If diaries only report the presence of crying during each hour slot, then each time slot is replaced by the corresponding median reported crying time for infants that were crying during that hour on that specific day of follow-up.

Secondary Outcome measure

Parent Confidence

Changes of parent confidence will be measured using the Parent Confidence Score at baseline and 14 day follow up. This score relies on 15 questions about parenting confidence with a likert scale of 4 choices (0 to 45 points). Changes over time will be measured at an individual level by adding the baseline value as a dependant variable in the mixed effect model. Movement of 6 points or more is to be considered as meaningful.

Global change

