This question asks about overall change in the infant's symptoms, from completely recovered to vastly worse. (Completely recovered, much improved, slightly improved, no change, slightly worse, much worse, vastly worse). These levels are coded numerically in an ordinal manner and are to be compared between groups using non-parametrical approaches.

Experience and satisfaction

Experience was measured using a 5-point likert scale from Very good, fairly good, neither good not bad, fairly poor and very poor.

Satisfaction was measured using a 5-point likert scale from Very satisfied, fairly satisfied, neither satisfied nor dissatisfied, fairly dissatisfied and very dissatisfied.

We also asked if the parent thought osteopathic care helped their baby using a yes, no or unsure response.

Unexpected and or Adverse events

We asked parents about additional care they may have administered to their infants and additional health care consultations they sought during the trial period as a proxy indicator of adverse events, and we also asked directly about any changes in symptoms that cause the parent concern. These included more distress, more crying, more unsettled, more vomiting, increased difficulty in feeding, sleeping and anything else (other).

Serious adverse events are reported by parents and managing osteopaths. These are assessed by the trial managing group and coded as for the reason for being a SAE and the estimated likelihood these are related to the treatment.

6. Randomisation

Block randomisation with variable block size of 4 and 6 generated by CastorEDC.

7. Sample size

From data collected during the pilot phase (n=13), we confirmed crying times as expected by Wolke et al. We estimate the average daily crying time over the two-week follow-up period to be of 120 minutes with a SD of 45 minutes. To detect a minimum of 30 minutes additional reduction in crying time between the intervention and control group with 90% power and a two-sided 5% significance level we would need 48 infants in each arm of the trial. If we allow for a 15% drop out we would need to randomise 112 infants, 66 in each arm of the trial. This sample size calculation is conservative because it disregards the fact that there are repeated measures in each infant and that the model will be corrected for the baseline crying time value. Thus, the actual power will be higher.

| Power | MCID (daily reduction in crying time in minutes) | | | |

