|--------------|---|-----------|-----------|-----------|
| | 10 | 15 | 30 | 60 |
| 0.8 | 636 | 284 | 72 | 18 |
| 0.9 | 852 | 380 | 96 | 24 |
| 0.95 | 1054 | 468 | 118 | 30 |

Table 4 : Sample size estimates without loss to follow up.

8. Statistical Analysis

All analysis will be intent-to-treat except for a secondary per protocol analysis on the primary outcome. All *P* values will be two sided, and the significance level is set at 5%. We will use STATA15 to precode the entire analysis prior to data collection (.do file). Deviations from the initial statistical plan will be recorded on the statistical output report.

Computing new variables

Protocol deviation

A new variable will be computed to identify deviations from protocol. Any participant who dropped-out, missed out a planned treatment, received external osteopathic care during the follow-up, or did not complete the diary daily are considered as participants who deviated from the protocol.

Unexpected reactions and adverse events

Serious adverse events, sae, will be reported as a total number for each group and as a risk ratio.

Serious adverse events will be monitored throughout the trial and reported by either the osteopaths or the participant parent.

Detailed reporting of unexpected reactions from follow-up and from the follow-up questionnaire are to be summarised to describe the presence of any unexpected reactions during the follow-up period.

Treatment description

A new set of variables is to be merged from detailed description of treatments during each visit and summarize whether each subset of care was provided or not.

Parent confidence scale

Parent confidence scale at baseline (pcs_b) and at 14 days (pcs_e) are computed from the 15 individual questions. Likert scales are scored 0 to 3 points. Scores for Q13 are inverted. Values for not applicable in Q1 and Q9 are given the score of 2. The points are then added up.

For descriptive purposes, the parent confidence scale at baseline can be compared with the following ranges:

- Non-clinical range 40 or more
- Mild clinical range 36-39
- Moderate clinical range 31-35
- Severe clinical range 31 or less

Missing data

Where participants withdraw, we will compare the characteristics of those withdrawing against those who remain in the study. Furthermore, we will do an:

- overall descriptive analysis of missing data searching for patterns,
- compare between group differences in missing data,

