- Analyse potential correlations between missing data in diary and overall summary measures.

Missing data for hourly entries will not be replaced (e.i. not missing total at random) unless parents did not report minutes in an explicit was. Graphical representations are replaced by estimates of hourly crying time. Reported crying within a hourly time slot without specification on the duration is replaced by the median observed crying time from other reported crying for that specific time slot (i.e. hour of the day and day of the trial).

Given the nature of the analysis, missing data within the diary will only reduce the power but should not affect the overall analysis.

For a diary to be considered, at least 7/14 days need to be filled in. Furthermore, best-case, and worst-case scenario will be simulated for the primary outcome implementing lowest and highest values for missing data (see sensitivity analysis).

Descriptive analysis

Descriptive statistics will be used to summarise the characteristics of participants in each arm of the trial. This will include baseline values, treatment schedules, compliance and follow-up. We will show number and percentage or mean and standard deviation for categorical and normally distributed continuous variables respectively. For data severely deviating from a normal distribution, we will present median and interquartile ranges. Probability of observed between groups difference will be provided using either Fisher's exact test, Chi2 test, and or Student's t-test.

Primary outcome analysis

We will analyse the primary outcome of crying time (e.i. individual daily measures of mean crying time in minutes) using random-effects multilevel linear regression. Crying time will be entered as the response variable (dependant) and the link function is identity. Therefore, lack of independence for measures from the same participant will be accounted for. To improve statistical power, the following explanatory variables are to be added to improve the modelling of the between-group differences

- baseline crying time (continuous),
- expectations from treatment (ordinal)
- and age of infants at entry (continuous).

To account for missing data, the data can be categorized and treated as nominal.

Results will be reported as between group difference in crying time in minutes with a 95% confidence interval. Statistical inference for significance of effects of the intervention will be calculated using Wald Chi² test.

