Mixed effect linear regression will be used to test continuous secondary outcomes. Categorical response variables using Likert scales (i.e. global change, parent satisfaction) will be considered as ordinal and non-parametrical tests (Mann Whitney U test) will be used to test between group differences. When possible (results from fractional polynomials), the outcome is to be dichotomised and the link function will be logit. Between group changes in parenting confidence score will compare changes from baseline by entering baseline score as an explanatory variable.

Proportion of participants who reported at least one adverse event will be compared between groups using a Fisher exact test. The same approach will be used to compare unexpected reactions (distress, crying, unsettled, vomiting, difficulties feeding, difficulties sleeping, other).

For cost of treatment, we will determine the mean number of treatments per infants in the trial and per group, the mean number of treatments will be multiplied by the average cost of an osteopathic treatment in UK pounds, determined by the latest data from the Institute of Osteopathy census.

Descriptive exploratory analysis

- Analyse trends over time using fractional polynomials.
- Adjust for osteopath level variables if between osteopath heterogeneity.

- Description of eventual correlation between years of experience and treatment effects (i.e. analyse of trend and comparison for cut-off at 3 or less years versus 4 or more).
- Investigate eventual association between post-graduate training and treatment outcome (interaction term).

Complementary confirmatory analysis

- A sensitivity analysis without imputed median values for crying times in time slots were parents reported crying will be run.
- A sensitivity analysis to adjust for recruiting site (ESO, UCO, Private practice, Swiss and Australian sites).
- A sensitivity analysis is planned to verify that the observed results hold in the worst- and best-case scenarios for missing data. The 25th and 75th percentile are to be used to replace missing data (25th for one group and 75th for the other) before running the primary analysis.
- If baseline imbalance (p -value <0.10) is observed, a secondary analysis with adjustment for these variables will be run to confirm results.

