- A sensitivity analysis adjusting for number of sessions, counselling and adjunctive treatment will be done to verify that the observed differences are not due to imbalance in patient management other than the tested intervention.
- Per protocol analysis.

9. Results analysis

Provisional tables

Table 1 Baseline characteristics for each group. GTR=, TTR=, SD=standard deviation

| Characteristics | Test group (GTR) N=xx | Control group (TTR) N= xx | Group imbalance (p-values) |
|---|-----------------------------|---------------------------------|----------------------------------|
| Females; n (%) | | | |
| Age of infant; n (%) | | | |
| 1–14 days (1–2 weeks) | | | |
| 15–28 days (3–4 weeks) | | | |
| 29–42 days (5–6 weeks) | | | |
| 43–56 days (7–8 weeks) | | | |
| 57–70 days (9–10 weeks) | | | |
| 71–84 days (11–12 weeks) | | | |
| Infant weight in kg; mean (SD) | | | |
| At birth | | | |
| At baseline | | | |
| Excessive crying, distress or unsettlement prior 24h; mean (SD) | | | |
| Age of mother in years; mean (SD) | | | |
| Siblings; n (%) | | | |
| None | | | |
| 1 | | | |
| 2 | | | |
| 3 or more | | | |
| Co-parenting; n (%) | | | |
| Parenting Confidence Score; n (%) | | | |
| Non-clinical range (40 or more) | | | |
| Mild clinical range (36-39) | | | |
| Moderate clinical range (32-35) | | | |
| Severe clinical range (31 or less) | | | |
| Expected response to osteopathic care; n (%) | | | |
| Very well | | | |
| Well | | | |
| Unsure | | | |
| Not very well | | | |
| Not well | | | |
| Missing | | | |

* Significant group imbalance at baseline

Table 2 Effects of treatment on crying time in minutes

| Outcomes | Test group (TTR) N=xx | Control group (GTR) N= xx | Adjusted * between group difference | Unadjusted between group difference |
|----------------------------------|------------------------------|---------------------------------|--|--|
| | Mean (Std.Err) | Mean (Std.Err) | Mean (CI 95%; P-value) | Mean (CI 95%; P-value) |
| Mean daily crying time (minutes) | | | | |
| From day 1 to day 13 | | | | |
| From day 1 to day 6 | | | | |
| From day 7 to day 13 | | | | |
| Daily crying times (minutes) | | | | |
| Day before treatment | | | | |
| Treatment day | | | | |
| Days after treatment | | | | |
| Day 1 | | | | |
| Day 2 | | | | |
| Day 3 | | | | |
| Day 4 | | | | |
| Day 5 | | | | |
| Day 6 | | | | |
| Day 7 | | | | |
| Day 8 | | | | |
| Day 9 | | | | |
| Day 10 | | | | |
| Day 11 | | | | |
| Day 12 | | | | |
| Day 13 | | | | |

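### One supportive analysis chooses its covariates by baseline tests at p<0.10, which selects by chance and not by prognostic value; the primary model is unaffected

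*SAP*

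**What the plan says.** The fourth of six items under Complementary confirmatory analysis in SAP section 8 reads: "If baseline imbalance (p -value <0.10) is observed, a secondary analysis with adjustment for these variables will be run to confirm results". The tests come from Descriptive analysis in the same section: "Probability of observed between groups difference will be provided using either Fisher's exact test, Chi2 test, and or Student's t-test". Provisional Table 1 in section 9 has a p-value column for group imbalance and a footnote mark for "Significant group imbalance at baseline".

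The rule gives no list of candidate variables, no prognostic criterion and no functional form. It does not say whether the selected variables join the primary covariates or replace them.

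The primary model is separate. Section 5 specifies a mixed model "adjusting for baseline crying time, expectations for treatment outcome and infant's age is used to estimate the between group difference". The same three covariates appear under Primary outcome analysis in section 8 and in the footnote to Table 2. On allocation, section 6 states: "Block randomisation with variable block size of 4 and 6 generated by CastorEDC".

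**The concern.** Among all infants randomised, baseline differences between arms arise by chance. A test of that difference measures how unusual the chance split is, and says nothing about how strongly the variable is related to crying time. Adjustment is worth having when a variable is prognostic. Under this rule, a strong predictor with a modest imbalance stays out and an irrelevant variable with a chance imbalance comes in.

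The analysis is meant to confirm the primary result. If chance decides whether it is run and what it contains, a reader cannot tell what its agreement or disagreement with the primary model shows.

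**Working it through.** **Inputs.** Threshold 0.10 (section 8). Table 1 lists 10 characteristics: sex, infant age, birth weight, baseline weight, crying in the prior 24 hours, mother's age, siblings, co-parenting, parenting confidence and expected response. Three of these (infant age, crying, expected response) are in the primary model, which leaves 7. Treating those 7 as the candidates is an assumption, because the rule names none.

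**The plan's own figure.** The plan gives no figure for this rule. The check uses its sample size, so that was reproduced first: n per arm = 2 × (1.960 + 1.282)² × (45/30)² = 2 × 10.51 × 2.25 = 47.3, rounded up to 48, as section 7 states.

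**Chance that the analysis is triggered.** With k independent tests, each at exactly 10% under randomisation:

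- k = 7: 1 − 0.9⁷ = 1 − 0.478 = 0.522, with 7 × 0.1 = 0.7 variables expected. Two or more: 1 − 0.478 − 7 × 0.1 × 0.9⁶ = 1 − 0.478 − 0.372 = 0.150.
- k = 6, if two candidates (for example the two weights) in effect count as one: 1 − 0.9⁶ = 0.469.

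**What the rule selects, and its effect on the estimate.** Simulation of 10,000 trials per setting: 48 per arm, no treatment effect, 7 independent normal candidates, t-tests at 0.10. One candidate is correlated with the outcome at 0.3, 0.5 or 0.7 (assumed values; the SAP gives none). The three primary covariates were not included. SDs of the treatment estimate are in units of the outcome SD.

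| Correlation | Prognostic variable selected | Other variables selected | SD: unadjusted | SD: p<0.10 rule | SD: pre-specified | Type I error: rule | Type I error: pre-specified |
|---|---|---|---|---|---|---|---|
| 0.3 | 9.7% | 10.1% | 0.205 | 0.205 | 0.196 | 4.8% | 5.1% |
| 0.5 | 10.5% | 9.9% | 0.204 | 0.196 | 0.177 | 4.0% | 5.0% |
| 0.7 | 9.7% | 10.2% | 0.202 | 0.183 | 0.145 | 3.2% | 4.9% |

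Selection rates are the same for prognostic and non-prognostic variables, so the prognostic one is omitted in about 1 − 0.10 = 90% of trials. At correlation 0.5 the rule recovers (0.204 − 0.196)/(0.204 − 0.177) = 0.008/0.027, about 30% of the available reduction in SD. At 0.7 it recovers 0.019/0.057, about 33%, and at 0.3 none. Type I error under the rule stays below the nominal 5% throughout.

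**The case against.** The strongest reply is that little depends on the rule. It governs one of six complementary analyses and cannot alter the primary estimate or its test. The groups are coded A and B until the final coding is validated (sections 3 and 4), so there is little room to favour one arm. The simulation shows no inflation of type I error, and precision is no worse than with no adjustment. All of this stands, and it limits the point to a supportive analysis.

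Several stronger readings are tempting, but the SAP does not support them:

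- *The adjusted model is left open.* Table 2's adjusted column uses three named covariates. Only the complementary model is unfixed.
- *The analysis will usually be triggered, with 65% probability.* That figure is 1 − 0.9¹⁰ and counts the three variables already in the primary model. The relevant figure is 52%, itself towards the upper end because the two weights are plausibly correlated and Fisher's exact test tends to fall below its nominal level.
- *The analysis cannot be pre-coded.* A p<0.10 rule can be scripted once candidates, tests and forms are named. What is missing is that list. The form matters: Table 1 shows parenting confidence in bands while section 5 defines a 0 to 45 score, and tests on the two could fall on opposite sides of 0.10.
- *It will contradict the primary result.* No rate of disagreement was calculated. If the selected variables join the primary three, the estimate remains a valid one.

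A further objection is that imbalance need not be pure chance in the analysed set, since a diary counts only with at least 7 of 14 days filled in and 15% dropout is allowed for. The SAP does not say which set Table 1 describes, so this is fair. It does not rescue the rule, because a p-value in that set still does not show whether a variable predicts crying time.

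**Conclusion.** The point holds for the baseline-imbalance item under Complementary confirmatory analysis, and only there. The rule omits a prognostic variable about 90% of the time. It triggers the analysis with probability about 52%, assuming the 7 remaining Table 1 variables are the candidates and their tests are independent; the true figure is somewhat lower. In the simulated settings it gains at most about a third of the precision that pre-specified adjustment would give. That result depends on the assumed correlations and on a simulation without the primary covariates.

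The harm is in lost precision and interpretation. Type I error is not inflated, and the primary result is untouched. The change is still worth making, because a better method is available at almost no cost.

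**What to change.** Delete the p<0.10 trigger. In its place, name a short set of additional covariates, drawn from those already collected and judged prognostic for crying time, with the form of each (continuous score or bands). The SAP offers no evidence on which of these predict crying, so the trial team must make and record that judgement before looking at baseline data by coded group. State that these covariates are added to the three primary ones, and that the analysis is run whatever the baseline table shows.

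Keep recruiting site where it is: it already has its own unconditional sensitivity analysis in the same list. Describe baseline imbalance by its size. Dropping the p-value column and significance footnote from Table 1 is optional, since that column alone changes no estimate.

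The cost is a few lines of SAP text and one fixed model in the analysis code. No further data are needed.

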* Adjusted for baseline crying time, infant age and prior expectations for osteopathic care

Table 3 Effects of treatment on other outcomes including undesirable events

| Outcomes | Test group (TTR) | Control group (GTR) | Between group difference* |
|--|---------------------|------------------------|------------------------------|
| | N=xx | N= xx | (CI 95%; P-value) |
| Parenting Confidence Score [0–45]; mean (SD) | | | |
| Perceived changes in symptoms; n(%) | | | |
| Completely recovered | | | |
| Much improved | | | |
| Slightly improved | | | |
| No change | | | |
| Slightly worse | | | |
| Much worse | | | |
| Vastly worse | | | |
| Weight changes over 14 days (kg); mean (SD) | | | |
| Satisfaction with received care; n (%) | | | |
| Very satisfied | | | |
| Fairly satisfied | | | |
| Neither satisfied nor dissatisfied | | | |
| Fairly dissatisfied | | | |
| Very dissatisfied | | | |
| Unexpected reactions; n(%) | | | |
| More distress | | | |
| Crying more | | | |
| More unsettled | | | |
| Vomiting more | | | |
| Increased feeding difficulties | | | |
| Increased difficulties sleeping | | | |
| Other | | | |
| Serious adverse events; n(%) | | | |
| Death | | | |
| Hospitalisation | | | |
| Long lasting morbidity | | | |
| Any | | | |

* P-values measured using likelihood ratio test in linear/logistic regression, Mann-Whitney U test for ordinal outcomes, Chi2 for categorical

Table 4 Number of sessions, advice given, additional treatment and effectiveness of blinding

| | Test group (TTR) N=xx | Control group (GTR) N= xx | Between group difference* |
|--|---------------------------|---------------------------------|------------------------------|
| | Mean (SD) | Mean (SD) | (CI 95%; P-value) |
| Number of sessions; mean (SD) | | | |
| Advices; n(%) | | | |
| Managing the baby's sleep pattern | | | |
| Managing the baby's feeding pattern | | | |
| Mother's diet | | | |
| Handling the baby | | | |
| Managing the baby's environment | | | |
| Parenting behaviour | | | |
| Reassure parent/guardian | | | |
| Other | | | |
| Medication and remedies; n(%) | | | |
| Prescribed medication | | | |
| Anti-gas drops | | | |
| Herbal supplements | | | |
| Probiotics | | | |
| Non-cow or anti-allergenic formula milk | | | |
| Omeprazol | | | |
| Other | | | |
| Additional care; n(%) | | | |
| General practitioner | | | |
| Accident and Emergency | | | |
| Unplanned hospital admission | | | |
| Another osteopath | | | |
| Paediatrician | | | |

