| Pharmacist | | | |
| Lactation consultation or midwife | | | |
| Other | | | |
| Blinding; n(%) | | | |
| Thinks the baby was in test group (TTR) | | | |
| Thinks the baby was in the control group (GTR) | | | |
| Doesn't know / unsure | | | |

* Adjusted for baseline crying time. P-values measured using likelihood ratio test in liner/logistic regression

Provisional Figures

Figure 1 Flow chart of participant inclusion and follow-up

Figure 2 Average daily crying time during follow-up between groups

Figure 3 Types of manual care received over the treatment period

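### The Table 4 footnote applies an adjusted logistic likelihood ratio test to every binary row, with no rule for sparse rows such as A&E or unplanned admission

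*SAP*

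**What the plan says.** Section 9 of the SAP gives provisional tables. Table 4 covers sessions, advice, additional treatment and blinding. Its last column is headed for a between-group difference with 95% CI and P-value, and its single footnote reads "Adjusted for baseline crying time. P-values measured using likelihood ratio test in liner/logistic regression". Under that footnote stand 8 advice rows, 7 medication rows and 8 additional-care rows, 23 binary rows in all. They include A&E, "Unplanned hospital admission", another osteopath and omeprazole. No exact or penalised method, and no fallback for small counts, is named for this table.

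Other parts of the SAP treat similar data differently:

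- Section 8, Secondary outcomes analysis: "Proportion of participants who reported at least one adverse event will be compared between groups using a Fisher exact test", and the individual unexpected reactions follow the same approach.
- Section 8, Descriptive analysis, offers Fisher's exact, chi-squared or t-tests for between-group comparisons. Its scope includes treatment schedules, compliance and follow-up.
- Section 5, Unexpected and or Adverse events, says parents were asked about extra care they gave and about "additional health care consultations they sought during the trial period as a proxy indicator of adverse events".

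**The concern.** A likelihood ratio P-value relies on a large-sample chi-squared approximation, which is poor when a row holds only a few infants. If all events fall in one arm, the maximum likelihood odds ratio is infinite, and an ordinary regression fit returns a meaningless standard error. The rows most likely to be sparse are emergency and hospital care, and Section 5 gives those rows a safety reading.

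At stake is how these rows are reported. The same split could be called significant under the Table 4 footnote and clearly non-significant under the Fisher rule in Section 8. Without a stated rule, that choice might be made after the split is known.

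**Working it through.** **Arm size.** Section 7 assumes "120 minutes with a SD of 45 minutes" and a 30-minute difference: "with 90% power and a two-sided 5% significance level we would need 48 infants in each arm of the trial". Check: n = 2(1.960 + 1.282)² × 45²/30² = 47.3, so 48 per arm. The figure reproduces. For the randomised total of 112, equal arms hold 56 each. Section 7 prints 66 per arm, which does not agree with 112, so 66 is also tried below.

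**Event counts.** The SAP gives none for Table 4 rows. The splits and rates below are assumptions, shown as a range.

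**One split: 3 versus 0, 48 per arm, unadjusted.**

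- Likelihood ratio: G = 2[3 ln(3/48) + 45 ln(45/48) − 3 ln(3/96) − 93 ln(93/96)] = 4.256 on 1 df, P = 0.039.
- Fisher: P = 2 × C(48,3)/C(96,3) = 2 × 17,296/142,880 = 0.242.

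| Split | Per arm | Likelihood ratio P | Fisher P |
|---|---|---|---|
| 2 v 0 | 48 | 0.093 | 0.49 |
| 3 v 0 | 48 | 0.039 | 0.24 |
| 3 v 0 | 56 | 0.039 | 0.24 |
| 3 v 0 | 66 | 0.040 | 0.24 |
| 4 v 0 | 48 | 0.017 | 0.12 |
| 5 v 0 | 48 | 0.007 | 0.056 |
| 6 v 0 | 48 | 0.003 | 0.027 |

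The arm size hardly matters. The two tests fall on opposite sides of 5% for 3, 4 or 5 versus 0.

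**Adjustment.** The footnote's test includes baseline crying time. Adding one unrelated normal covariate to a 3 v 0 split (2,000 simulated data sets per arm size) gave a median P of 0.039. P was below 0.05 in 91% of data sets at both 48 and 56 per arm.

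**Error rate.** Both arms share the same true rate, and all pairs of binomial counts are enumerated. The test is unadjusted and two-sided at 5%.

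| True rate | Likelihood ratio, 48 / 56 per arm | Fisher, 48 / 56 per arm |
|---|---|---|
| 1% | 1.5% / 2.1% | 0.0% / 0.0% |
| 2% | 5.4% / 6.6% | 0.0% / 0.1% |
| 3% | 8.3% / 9.0% | 0.2% / 0.3% |
| 4% | 9.2% / 9.2% | 0.4% / 0.6% |
| 5% | 8.9% / 8.4% | 0.7% / 0.9% |
| 10% | 6.1% / 6.0% | 1.7% / 2.0% |

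**Error rate given the row total.** At 48 per arm the unadjusted likelihood ratio test rejects by chance in 0% of cases with 1 or 2 events, 24% with 3 (the Fisher calculation above), 12% with 4, 5.6% with 5 and 2.7% with 6.

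**Interval.** For 3 v 0 at 56 per arm, with one covariate in the model, the fitted log odds ratio stopped at 21.7 with a standard error of about 17,500, so a Wald interval is unusable. Inverting the unadjusted likelihood ratio test gives an odds ratio interval from about 1.15 with no upper limit.

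A risk difference stays finite. For 3/48 v 0/48, d = 6.25%. The Wilson limits are 2.1% to 16.8% and 0% to 7.4%. The Newcombe limits are 6.25 − √((6.25 − 2.15)² + 7.41²) = −2.2 points and 6.25 + (16.84 − 6.25) = 16.8 points.

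**The case against.** The strongest reply is that the body of Section 8 already allows Fisher's exact test for descriptive comparisons, and much of Table 4 is that kind of material. On this view the defect is a mismatch between a provisional footnote and the text. That stands in part. Section 8 permits Fisher's test but does not name additional care, while the footnote is specific to Table 4 and names only the likelihood ratio test.

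Second, admissions have their own safety route. The SAE dataset codes unexpected hospital admission as a level of seriousness, Section 8 reports SAEs as totals and a risk ratio, and Table 3 has a hospitalisation row. A reader might infer that the trial's safety conclusion on admissions depends on the Table 4 test. The SAP does not support that.

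Three other strong readings are tempting:

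- That 3 v 0 is always declared significant. The planned test is adjusted, and 9% of the simulated data sets did not reach 0.05.
- That no confidence interval exists at all. A profile-likelihood interval does, but it has no upper limit.
- That the likelihood ratio test is too liberal whenever events are few. At a 1% rate it rejects less often than 5%, and with 1 or 2 events it cannot reject without adjustment.

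The 24% figure for three events is the worst case among small totals, not a typical value.

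Finally, the method need not be replaced for every binary row. At a 10% rate the likelihood ratio test's error is about 6% and Fisher's is 2% or less. For common rows the choice is a matter of preference.

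**Conclusion.** The concern holds in limited form. The Table 4 footnote has no rule for sparse binary rows, and it does not match the Fisher approach of Section 8 for adverse events, for which Section 5 makes additional care a proxy. If a row holds only a few infants, a 3 v 0 split would usually be called significant (P=0.039 unadjusted) where Fisher's test gives 0.24. The unadjusted error rate is about 5-9% at event rates of 2-5%.

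This rests on three assumptions: that some rows will be that sparse, which the SAP neither states nor excludes; that arms are roughly equal; and that the unadjusted error rates approximate the adjusted test, whose error rate was not computed. The primary crying-time conclusion is unaffected. The point deserves correction because it changes the P-values and intervals reported for emergency and hospital care.

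**What to change.** Amend the Table 4 footnote so that sparse binary rows, for example those with any expected cell count below 5 or no event in one arm, report n (%), Fisher's exact P-value and an unadjusted risk difference with a Newcombe or exact 95% CI. With equal arms, an expected count below 5 means fewer than 10 events in the row. Keep the adjusted regression for the number of sessions and for the common rows. Settle the rule before group identity is revealed.

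The cost is one footnote and a few lines of code. Fisher's test is conservative, as the error-rate table shows, and the adjustment for baseline crying time is lost for those rows. With so few events that adjustment can offer little.
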